### **5.3. Medical History**

Medical history collected at screening will not be coded. Medical history will be summarized by treatment groups. Numbers and percentages of subjects who experienced myocardial infarction before the age of 50 years, experienced stroke before the age of 50 years, and have diabetes (type I or II) will be provided. Reported medical condition terms of subject having any relevant medical history, including any medication allergies, will be presented by descending order of the total frequencies. Same reported terms will be counted only once in the summary. The summary will be provided for the Safety Analysis Set. No formal statistical testing is planned.

A by-subject listing of disease-specific medical history will be provided by treatment group and subject ID number (in ascending order) and medical history of abnormalities (in chronological order).

## 6. EFFICACY ANALYSES

### 6.1. General Considerations

The primary analysis set for efficacy analyses will be the FAS, defined in Section 3.1.2.

If multiple valid, nonmissing efficacy measurements exist in an analysis window, records will be chosen based on the following rules if a single value is needed:

- If record collection date/time is known, latest record will be taken
- If time is unknown, the worst scenario will be selected

For the composite endpoints including DAS28(CRP), ACR 20/50/70, SDAI, and CDAI, we use the following steps unless otherwise specified:

- Step 1: Put each component value into a visit window
- Step 2: Within each visit window, select the component data point for analysis
- Step 3: Combine these selected data points within each visit window across the components.

Below are the descriptions for the imputation methods that will be used throughout the efficacy analyses:

- Observed case (OC): missing values remain missing. For the above composite endpoints, in the case that some components are missing, the composite endpoint assessment will be derived based on the non-missing components. If non-missing components are not sufficient to determine final composite endpoint, then the composite endpoint will be considered as missing.
- Last observation carried forward (LOCF): For the above composite endpoints, First LOCF all components over all visits, then combine the components as mentioned above.
- Non-responder imputation (NRI): For all binary response measurements, starting from OC, all missings will be treated as non-responders.

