**Figure 1-1.**

**Study Schema**

Following completion of screening assessments, eligible subjects will be randomized in a blinded fashion in a 1:1:1:1 ratio as follows (all groups will continue to take MTX):

- GS-9876 30 mg:** GS-9876 (1 x 30 mg tablet QD) + placebo-to-match (PTM) filgotinib (2 x placebo tablets QD) (N=20)
- GS-9876 10 mg:** GS-9876 (1 x 10 mg tablet QD) + PTM filgotinib (2 x placebo tablets QD) (N=20)
- Filgotinib 200 mg:** Filgotinib (2 x 100 mg tablets QD) + PTM GS-9876 (1 x placebo tablets QD) (N=20)
- Placebo only:** PTM GS-9876 (1 x placebo tablet QD) + PTM filgotinib (2 x placebo tablets QD) (N=20)

Randomization will be stratified by prior inadequate response to biologic therapy and geographic region.

Subjects will be dosed for up to 12 weeks and then followed for 4 weeks after their last dose of study drug.

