#### **3.7.2. Analysis Visit Windows**

Subject visits may occur on days not specified in the protocol (eg, unscheduled visits). Therefore, for the purpose of analysis, observations will be assigned to analysis windows.

In general, the baseline value will be the last nonmissing value on or prior to the first dose date of study drug.

**Table 3-1 Analysis Visit Windows for Joint Count Assessment, HAQ-DI, PhGA, PtGA, and On-Treatment CRP, Safety Laboratory Data, Weight, Vital Signs, ECG**

Nominal Visit	Nominal Study Day	Lower Limit	Upper Limit
Baseline	1	(none)	1
Week 2	15	2	22
Week 4	29	23	43
Week 8	57	44	71
Week 12	85	72	≥ 85

The analysis windows for joint count assessment, health assessment questionnaire - disability index (HAQ-DI) (including the patient’s assessment of pain), physician’s global assessment of disease activity (PhGA), patient’s global assessment of disease activity (PtGA), on-treatment CRP, safety laboratory, weight, vital signs and electrocardiogram (ECG) are provided in [Table 3-1](#). CRP, safety laboratory, weight, vital signs, and ECG data collected up to the last dose date of any study drug + 3 days are considered to be on-treatment data.

CRP, safety laboratory, weight, vital signs, and ECG data collected after last dose date of any study drug + 3 days will be considered as posttreatment data and will be summarized up to last dose date plus 30 days, and labeled as “FU-Week 4”. Data obtained after last dose date plus 30 days will be excluded from the summaries, but will be included in the listings.

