### **3.7.3. Selection of Non-Efficacy Data in the Event of Multiple Records in an Analysis Visit Window**

Depending on the statistical analysis method, single values may be required for each analysis window. For example, change from baseline by visit usually requires a single value, whereas a time-to-event analysis would not require 1 value per analysis window.

If multiple valid, nonmissing, continuous measurements exist in an analysis window, records will be chosen based on the following rules if a single value is needed:

- In general, the baseline value will be the last nonmissing value on or prior to the first dose date of study drug, unless otherwise specified. If multiple measurements occur on the same day, the last nonmissing value prior to the time of first dose of study drug will be considered as the baseline value. If these multiple measurements occur at the same time or the time is not available, the average of these measurements (for continuous data) will be considered the baseline value.
- For postbaseline visits:
  - The record closest to the nominal day for that visit will be selected.
  - If there are 2 records that are equidistant from the nominal day, the later record will be selected.
  - If there is more than 1 record on the selected day, the average will be taken, unless otherwise specified.

If multiple valid, nonmissing, categorical measurements exist in an analysis window, records will be chosen based on the following rules if a single value is needed:

- For baseline, the last available record on or prior to the date of the first dose of study drug will be selected. If there are multiple records with the same time or no time recorded on the same day, the value with the lowest severity will be selected (eg, normal will be selected over abnormal for safety ECG findings).
- For postbaseline visits:
  - The record closest to the nominal day for that visit will be selected.
  - If there are 2 records that are equidistant from the nominal day, the later record will be selected.
  - If there is more than 1 record on the selected day, the value with the worst severity will be taken (eg, abnormal will be selected over normal for safety ECG findings), unless otherwise specified.

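### The latest-record rule for efficacy data, with an open-ended Week 12 window and a post-dose cut-off that among efficacy components covers only CRP, lets a later assessment replace the Day 85 value

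*SAP*

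**What the plan says.** Section 6.1 of the SAP sets the selection rule for multiple efficacy records in a window: "If record collection date/time is known, latest record will be taken". Its fallback is: "If time is unknown, the worst scenario will be selected". The same section builds composite endpoints by selecting each component separately within the window and then combining the selected values.

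Other data follow a different rule. Section 3.7.3 says of postbaseline visits: "The record closest to the nominal day for that visit will be selected", with the later record kept in a tie. Its title limits it: "Selection of Non-Efficacy Data in the Event of Multiple Records in an Analysis Visit Window".

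Table 3-1 in Section 3.7.2 applies one set of windows to joint counts, HAQ-DI, the physician's and patient's global assessments (PhGA, PtGA), CRP and the safety measures. Its last row reads "Week 12 85 72 ≥ 85" (visit, nominal day, lower limit, upper limit). Section 3.7.2 also expects unscheduled visits and assigns them to windows. Its on-treatment definition covers "CRP, safety laboratory, weight, vital signs, and ECG data collected up to the last dose date of any study drug + 3 days"; later values of those measures go to a separate follow-up row. Joint counts, HAQ-DI, PhGA and PtGA are not in that list. On follow-up, the design section states: "Subjects will be dosed for up to 12 weeks and then followed for 4 weeks after their last dose of study drug".

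**The concern.** Week 12 is the time point of the primary endpoint (Section 6.2.1) and of both secondary endpoints (Section 6.3). Under these rules a valid Day 85 assessment is set aside whenever a later record of the same measure exists, however much later and whether or not the subject is still on study drug. The value reported as Week 12 may then describe another time or an off-drug state.

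The cut-off also treats the components of one score differently. CRP stops 3 days after the last dose while joint counts and PtGA do not, so a DAS28(CRP) value could combine measurements taken weeks apart. HAQ-DI contains no CRP and has its own Week 12 model, so it is exposed on its own.

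No planned analysis would show the effect. Section 6.2.4 rules out sensitivity analyses of the primary endpoint, and the LOCF analysis of ACR20 concerns missing data, not the choice among existing records.

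**Working it through.** **1. Lateness that the rule permits.** Inputs: Table 3-1. Formula: upper limit minus nominal day.

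- Week 2: 22 − 15 = 7 days
- Week 4: 43 − 29 = 14 days
- Week 8: 71 − 57 = 14 days
- Week 12: no upper limit, so no bound. An assessment 28 days after a last dose on Day 85 would fall on Day 113, inside the window.

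**2. The two selection rules on example records.**

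| Window | Record days | Latest (6.1) | Nearest (3.7.3) |
|---|---|---|---|
| Week 2 | 15, 20 | 20 | 15 |
| Week 4 | 29, 40 | 40 | 29 |
| Week 8 | 57, 70 | 70 | 57 |
| Week 12 | 85, 95 | 95 | 85 |
| Week 12 | 85, 113 | 113 | 85 |
| Week 12 | 75, 85 | 85 | 85 |
| Week 12 | 86 (unscheduled), 92 (scheduled) | 92 | 86 |

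The sixth row shows that an earlier extra record displaces nothing under either rule. The last row shows that the nearest-day rule can also prefer an unscheduled record (1 day from nominal against 7).

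**3. The cut-off.** With a last dose on Day 85, on-treatment CRP ends on Day 85 + 3 = 88. Joint counts and PtGA recorded on Day 113 would still be in the Week 12 window, so DAS28(CRP) could join a Day 85 CRP to Day 113 clinical components. For an early stopper, a record 28 days after a last dose on Day 57 falls on Day 57 + 28 = 85. Both selection rules accept it as Week 12.

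**4. The plan's power.** Section 1.3 gives a difference of 1.2, SD 1.35, 20 per group and a 2-sided 0.05 level. The standard error is 1.35 × √(2/20) = 0.43 and the noncentrality 1.2 / 0.427 = 2.81. The two-sample t-test (38 degrees of freedom) has 78.2% power, which reproduces the stated 78%. The record-selection rule does not alter this calculation.

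**5. Illustrations only.** None of the following inputs is in the SAP.

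*Attenuation.* Let f be the share of subjects whose Week 12 value is displaced by an off-drug record and L the share of the effect lost in them, with the SD unchanged. The difference becomes 1.2 × (1 − f × L). For L = 50%:

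| f | Difference | Power |
|---|---|---|
| 10% | 1.14 | 74% |
| 25% | 1.05 | 67% |
| 50% | 0.90 | 54% |
| 100% | 0.60 | 28% |

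*Inflation.* Suppose 2 of 20 placebo subjects and no GS-9876 subjects have a later record that is worse than the scheduled one. If it is worse by 1.0 DAS28 unit, the difference grows by 2/20 × 1.0 = 0.10, which is 8% of 1.2 and 0.10 / 0.43 = 0.23 standard errors. If it is worse by 0.5 HAQ-DI units, the difference grows by 2/20 × 0.5 = 0.05.

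**The case against.** Section 6.1 is explicit and reproducible, and latest-in-window is a convention that a plan may choose. A reader might infer that it contradicts Section 3.7.3. It does not, because the title of Section 3.7.3 confines it to non-efficacy data. This objection stands.

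A reader might also infer that off-drug follow-up values routinely overwrite Day 85. The SAP does not support that: it nowhere says that joint counts or HAQ-DI are collected at the 4-week follow-up. The title of Table 3-1 puts the on-treatment label on CRP and the safety measures only, which hints that the other four have no scheduled post-treatment assessment. The visit schedule belongs to the protocol, which is not at hand.

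Nor can a direction of bias be read from the document. It does not say that unscheduled visits follow worsening, that efficacy is assessed at them, or that they are commoner on placebo. Attenuation and inflation are both possible.

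Three further points are fair. Nearest-day selection alone does not remove off-drug records in early stoppers. The by-subject listings promised in Section 3 should show the extra records, so they are not hidden altogether. The limited shifts at Weeks 2, 4 and 8 concern visits that are not named primary or secondary time points.

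What remains is that the SAP itself expects unscheduled visits, and nothing in it prevents a later efficacy record from replacing the Day 85 one.

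**Conclusion.** The point holds as a weakness in the analysis rules. Three provisions act together: latest-record selection, a Week 12 window with no upper end, and a post-dose cut-off that among the efficacy components reaches only CRP. Followed as written, they can label a record from another time, or from off drug, as Week 12 in the analyses of DAS28(CRP), ACR20/50/70 and HAQ-DI.

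The permitted lateness is certain from Table 3-1. The effect on the results is not: it depends on whether later assessments of these measures exist, in how many subjects, and how they differ by arm, none of which the SAP gives. The power and bias figures above therefore show sensitivity and are not estimates. CRP is protected against off-drug displacement, but a later on-treatment CRP would still replace the scheduled one when it enters a composite. The change is worth making because the affected endpoints are the main ones and the remedy is cheap.

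**What to change.** 1. In Section 6.1, replace latest-record selection for postbaseline efficacy data with the Section 3.7.3 rule: nearest to the nominal day, the later record if two are equidistant.
2. In Section 3.7.2, state one on-treatment or upper-limit rule that applies alike to all components of DAS28(CRP), ACR and HAQ-DI, and send records beyond it to the listings or a follow-up row. An upper limit alone keeps far-off records out for completers but leaves the early-stopper case (last dose Day 57, record Day 85). An on-treatment rule covers both. If off-drug values of early stoppers are meant to count, the SAP should say so.
3. Optionally, cap the Week 12 window at Day 98, which mirrors the lower limit (85 − 72 = 13; 85 + 13 = 98).

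The cost is a few lines of text and a small change to the derivation program. Sample size and stated power are unchanged. The downside is that any cut-off makes some late Week 12 visits missing. Under non-responder imputation (Section 6.3.2) such a subject may count as an ACR failure, and the MMRM (Section 6.2.3) has no Week 12 value for that subject. With 20 per group this is a reason to set the limit with care.

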#### 6.1.1. Tender/Swollen Joint Counts (TJC/SJC)

TJC68 and SJC66 will be collected during the course of the study. The assessment for each joint will be from the following selections: Tender Only, Swollen Only, Tender and Swollen, Not Tender or Swollen, or Joint Non-Evaluable or Missing.

Individual joint with missing assessment will not be imputed. If at least half of the joints are assessed at a given visit, the *prorated* tender and swollen joint counts will be calculated using the following formula:

$$TJC68 = \frac{\text{Total number of tender joints}}{68 - (\text{Number of nonevaluable or missing joints out of 68 joints})} \times 68$$

$$SJC66 = \frac{\text{Total number of swollen joints}}{66 - (\text{Number of nonevaluable or missing joints out of 66 joints})} \times 66$$

If less than half of joints are assessed at a given visit, joint counts are treated as missing for the visit.

A more abbreviated assessment considering 28 joints as listed in [Table 6-1](#) for both tenderness and swelling will also be conducted (as part of the TJC68 and SJC66 assessment), denoted as TJC28 and SJC28, respectively.

**Table 6-1. Composition of the 28 Joints**

Joint	Number
Shoulder Joints (Left and Right)	2
Elbow Joints (Left and Right)	2
Wrist Joints (Left and Right)	2
Metacarpophalangeal Joints I-V (Left and Right)	10
Proximal Interphalangeal Joints I-V (Left and Right)	10
Knee Joints (Left and Right)	2

If there are non-evaluable or missing joints among the 28 joints but at least half of the joints are assessed at a given visit, similar prorated tender and swollen joint counts will be calculated as follows:

$$TJC28 = \frac{\text{Total number of tender joints}}{28 - (\text{Number of nonevaluable or missing joints out of 28 joints})} \times 28$$

$$SJC28 = \frac{\text{Total number of swollen joints}}{28 - (\text{Number of nonevaluable or missing joints out of 28 joints})} \times 28$$

If less than half of the 28 joints are assessed at a given visit, TJC28 and SJC28 are treated as missing for the visit.

### **6.1.2. Global Assessment of Disease Activity**

The Patient's Global Assessment of Disease Activity is a horizontal (0 – 100) visual analog scale (VAS) that ranges from "No Arthritis" to "Severe Arthritis."

The Physician's Global Assessment of Disease Activity is a horizontal (0 – 100) VAS that ranges from "No Disease Activity" to "Maximum Disease Activity."

## **6.2. Primary Efficacy Endpoints**

### **6.2.1. Definition of the Primary Efficacy Endpoints**

The primary endpoint for the study is change from baseline in DAS28(CRP) at Week 12. The DAS28(CRP) score is calculated as follows:

**DAS28(CRP) = 0.56 $\sqrt{\text{TJC28}}$  + 0.28 $\sqrt{\text{SJC28}}$  + 0.36 ln(CRP + 1) + 0.014 × PtGA + 0.96,**  
where

TJC28 = number of joints tender out of 28 joints

SJC28 = number of joints swollen out of 28 joints

CRP = CRP measurement in unit of *mg/L*

PtGA = patient's global assessment of disease activity on a 0-100 VAS

Higher DAS28(CRP) value indicates more severe disease activity.

DAS28(CRP) will be calculated only for the time points with all measurements available.

### **6.2.2. Statistical Hypotheses for the Primary Efficacy Endpoints**

The primary analysis will consist of a superiority test at the 2-sided 0.05-level of each of the GS-9876 doses compared to placebo based on the change from baseline in DAS28(CRP) at Week 12. There is no adjustment for multiple testing for this study.

The mean change from baseline in DAS28(CRP) at Week 12 for treatment groups GS-9876 10 mg, GS-9876 30 mg and placebo group are denoted as  $\mu_1$ ,  $\mu_2$  and  $\mu_P$ , respectively.

The primary statistical hypotheses for the superiority tests are as follows:

$$H_0: \mu_1 = \mu_P \text{ vs } H_1: \mu_1 \neq \mu_P$$

and

$$H_0: \mu_2 = \mu_P \text{ vs } H_1: \mu_2 \neq \mu_P$$

### **6.2.3. Analysis of the Primary Efficacy Endpoint**

Change from baseline in DAS28(CRP) at Week 12 will be analyzed using a mixed-effects model for repeated measures (MMRM) approach. The model will include the fixed effects of treatment, visit, treatment by visit interaction, and baseline DAS28(CRP) value. Subjects will be included as a random effect. Missing change scores (eg, due to early withdrawal, etc.) will not be otherwise imputed using the MMRM approach. An unstructured variance-covariance matrix for the repeated measures and Kenward-Roger approximation for the denominator degrees of freedom will be used in the mixed-effects model.

From the MMRM approach, estimated differences in mean change from baseline between each of the GS-9876 doses and the placebo group will be presented with 95% confidence intervals (CIs) and p-values. **PPD**

Change from baseline in DAS28(CRP) will be summarized by treatment and visit using descriptive statistics (sample size, mean, SD, median, Q1, Q3, minimum, and maximum). Plots of mean  $\pm$  SD of DAS28(CRP) values and changes from baseline in DAS28(CRP) over time will be presented.

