## **3.3. Strata and Covariates**

Subjects will be randomly assigned to treatment groups via the IXRS in a 1:1:1:1 ratio using a stratified randomization schedule. Stratification will be based on the following variables:

- Geographic region (**Region 1** includes the United States; **Region 2** includes the following countries: Bulgaria, Ukraine, Czech Republic, Georgia, Hungary, Moldova, and Poland)
- Prior inadequate response to biologic therapy (Yes or No). In the eCRF data, subjects who discontinued prior RA biologic therapy before the first dose date of any study drug due to any of the following reasons are considered to have prior inadequate response to biologic therapy:
  - Primary inadequate response
  - Loss of response
  - Intolerance (Non-allergic)
  - Allergic response

Please refer to [Appendix 2](#) for the RA biologic therapy list.

If there are discrepancies in stratification factor values between the IXRS and the clinical database, the values derived from the clinical database will be used for analyses.

For efficacy endpoints, the baseline value of the efficacy variable(s) will be included as covariates in the efficacy analysis model, as specified in Section 6.

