### **6.2.4. Sensitivity Analysis of the Primary Efficacy Endpoints**

Sensitivity analyses of the primary efficacy endpoint will not be performed.

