#### 6.3.2. Analysis Methods for Secondary Efficacy Endpoints

The ACR20 response rates at Week 12 between each of the GS-9876 dosed groups and the placebo group will be compared using a stratified Cochran-Mantel-Haenszel (CMH) chi-square test adjusting for stratification factors in randomization (ie, prior inadequate response to biologic

therapy, yes vs. no; and Geographic region, region 1 vs. region 2 as defined in Section 3.3). The difference in response rates between treatment groups and the corresponding 95% CIs will be presented. The CMH chi-square p-value for testing the superiority of each of the GS-9876 doses as compared to placebo will be provided, as well as the 2-sided 95% exact CI of the ACR20 response rate based on Clopper-Pearson method for each treatment group. Subjects who do not have sufficient measurements to establish efficacy at Week 12 will be considered as failures (ie, non-responder imputation [NRI]). Sensitivity analysis will be conducted by imputing missing components for determining ACR20 as well as early dropouts via the last observation carried forward (LOCF) method.

[figure not shown]
For ACR50 and ACR70 at Week 12, the same CMH approach with NRI as in the analysis of ACR20 described above will be adopted.

The difference in change from baseline in HAQ-DI between each of the GS-9876 dosed groups and the placebo group will be analyzed using a similar MMRM approach as described in Section 6.2.3. The model will include the fixed effects of treatment, visit, treatment by visit interaction, and baseline value. Subjects will be included as a random effect. Missing change scores (eg, due to early withdrawal, etc) will not be otherwise imputed using the MMRM approach.

[figure not shown]
Mean ACR 20/50/70 response rates with NRI will be plotted by treatment and visit. Mean  $\pm$  SD over time will be plotted for each component of ACR 20/50/70.

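### The DAS28(CRP) and HAQ-DI mixed models leave out both randomisation strata, which costs precision if the strata are prognostic

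*SAP*

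**What the plan says.** The study schema text in SAP section 1.2 states: "Randomization will be stratified by prior inadequate response to biologic therapy and geographic region". Section 3.3 defines both factors as binary: Region 1 or 2, and biologic response yes or no. Where IXRS and the clinical database disagree, "the values derived from the clinical database will be used for analyses".

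The primary analysis is a "superiority test at the 2-sided 0.05-level of each of the GS-9876 doses compared to placebo" (section 6.2.2), made with the mixed model of section 6.2.3: "The model will include the fixed effects of treatment, visit, treatment by visit interaction, and baseline DAS28(CRP) value". Section 6.3.2 specifies HAQ-DI in the same way: "The model will include the fixed effects of treatment, visit, treatment by visit interaction, and baseline value". That section also compares ACR20 rates with a Cochran-Mantel-Haenszel "chi-square test adjusting for stratification factors in randomization", and ACR50 and ACR70 follow the same method.

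Section 3.3 names only one kind of covariate: "For efficacy endpoints, the baseline value of the efficacy variable(s) will be included as covariates in the efficacy analysis model". Section 6.2.4 closes the other route: "Sensitivity analyses of the primary efficacy endpoint will not be performed".

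**The concern.** The two factors govern the allocation and enter the ACR tests, yet they are absent from both continuous-endpoint models, one of which is the primary analysis. The SAP gives no reason. The fixed-effect sentences are complete, so the redactions nearby do not explain the gap. The by-stratum results planned in sections 3.4 and 6.2.5 give separate estimates within each stratum. They do not give one pooled, adjusted treatment difference.

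The issue is precision. Balancing the arms on a prognostic factor makes the estimated difference less variable. A model that ignores the factor still counts its spread as noise and reports a standard error that is too large. With 20 subjects per arm and planned power just under 80%, this proof-of-concept trial could miss an effect that its own design was able to detect.

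**Working it through.** **Inputs from the SAP.** Section 1.3: difference 1.2, common SD 1.35, 20 per arm, two-sided 0.05, stated power 78%. Section 1.2: four arms, 1:1:1:1. Not in the SAP: R², the share of residual variance that the two factors explain beyond the baseline score. It is therefore varied from 0 to 20%.

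**Step 1: reproduce the stated power.** The SE is 1.35 × √(2/20) = 0.427 and the noncentrality is 1.2 / 0.427 = 2.81. A two-sample t-test with 38 df gives 78.2%, which matches the SAP. The normal approximation gives 80.3%, so the planning figure is evidently a t-test without covariates. The omission of the strata does not affect it.

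**Step 2: what adjustment should give.** With both factors in the model, SE = 0.427 × √(1 − R²), with 2 fewer df (36). This is a two-arm t calculation.

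| R² (assumed) | SE with factors | Power with factors |
|---|---|---|
| 0% | 0.427 | 78.1% |
| 5% | 0.416 | 80.1% |
| 10% | 0.405 | 82.2% |
| 20% | 0.382 | 86.4% |

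**Step 3: what the model as written does.** This was simulated at a single visit: 80 subjects, four arms, permuted blocks of 4 within the 2×2 strata, baseline covariate, 60,000 runs. Block size and cell shares (12/8/50/30%) are assumed. Monte Carlo error is about 0.2 point for power and 0.1 point for type I error.

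| R² | Power without | Power with | Type I error without |
|---|---|---|---|
| 0% | 78.7% | 78.5% | 5.1% |
| 5% | 79.2% | 80.7% | 4.5% |
| 10% | 79.8% | 82.7% | 4.0% |
| 20% | 80.8% | 86.7% | 3.0% |

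With the factors in the model, type I error is 5.1% throughout. Without them, the mean reported SE is 0.430, while the true SD of the estimate is 0.411 at R² = 10% and 0.389 at 20%. The 95% CI half-width is about 0.86 as written, against 0.81 (10%) or 0.77 (20%) with the factors. A separate 20,000-run simulation with exactly balanced strata and other assumed cell sizes agrees: 80.2 vs 83.1% at 10% and 81.4 vs 87.1% at 20%.

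**Step 4: repeated visits.** A four-visit unstructured model was run with complete data, residual df in place of Kenward-Roger, and assumed visit SDs and correlations (2,000 runs, Monte Carlo error about 0.9 point). The stratum effect was assumed to grow as 25/50/80/100% over Weeks 2, 4, 8 and 12. Power with no strata, main effects, and strata-by-visit terms was:

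- R² = 10%: 78.6 / 80.1 / 81.4%
- R² = 20%: 81.6 / 84.8 / 86.2%

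If the stratum effect is constant over visits, main effects do as well as the interactions (86.8 vs 87.1% at 20%, against 81.5% without strata).

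**Step 5: misclassified strata.** If 15% of biologic-response values differ between IXRS and the database, and the analysis uses the database values, the gain remains: 79.4 vs 82.5% at 10% and 79.4 vs 85.7% at 20%.

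**The case against.** The strongest reply is that the analysis as written is valid. It is unbiased, does not inflate type I error and follows section 3.3 as worded. A stratified test for a binary endpoint beside a baseline-adjusted mixed model is a difference of method, not a contradiction. All of that is true, and it limits the point to efficiency.

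The second reply is that the size is assumed. The calculations above also treat 1.35 as the SD left after baseline adjustment, which section 1.3 does not say. If it is the SD before adjustment, the baseline covariate already raises power and less is left to gain. With baseline explaining 25% of variance (assumed), power without and with the strata is 89.9 vs 90.7% at R² = 5% and 89.3 vs 91.0% at 10%. With baseline explaining 15%, it is 85.1 vs 86.2% and 87.1 vs 89.1%. Each figure carries about 0.4 to 0.5 point of Monte Carlo error. The power gain is then about 1 to 2 points at 5–10%, and about 3 to 4 points at 20%. This stands as a caution about power. It does not touch the standard error, which remains too large by the same proportion.

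The third reply concerns strata-by-visit terms. Two factors across four visits add eight parameters in an 80-subject model with unstructured covariance. Stratum sizes are unknown, and section 3.4 itself allows for subgroups too small to model. The four-visit evidence in their favour is noisy. The interactions are therefore a preference only. Two main effects are cheap, and the SAP already accepts a four-cell stratified ACR test.

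**Conclusion.** The point holds. Both mixed models omit both stratification factors, and nothing else in the SAP supplies an adjusted estimate. If the factors explain 5–20% of residual variance, the achievable standard error is about 2.5–10.6% smaller than the one the model reports. The power forgone is about 1.5 to 6 points if 1.35 is the residual SD, and less if it is the SD before baseline adjustment. If the factors explain nothing, nothing is lost.

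These sizes rest on assumed R² values, assumed stratum shares and simplified models, so they are indicative for the planned mixed model. The SAP gives no planning figures for HAQ-DI; the same reasoning applies there, but its size was not calculated. The change is worth making because its cost is close to zero under every assumption tried. It is not a threat to the validity of the trial.

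**What to change.** In sections 6.2.3 and 6.3.2, add fixed effects for geographic region and for prior inadequate response to biologics to both mixed models. Main effects are the minimum. Their visit interactions are preferable if stratum sizes allow, because stratum effects may grow over time. In section 3.3, list the two factors as model covariates beside the baseline value, using the clinical-database values already specified there. If the sponsor prefers to keep the present primary model, it should state why and pre-specify the adjusted version as a supportive analysis, which means amending section 6.2.4.

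The cost is a line of text in each section and about two degrees of freedom at Week 12. If the strata are inert, the power cost is about 0.1 point in the single-visit calculation and about 0.5 point, within Monte Carlo error, in the four-visit one. No new data are needed. Because a separate unblinded team has already seen interim efficacy results (section 2.1), the change should be recorded as made by the blinded study team before database finalisation, and checked against the protocol's own description of the model.
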